10.2. Data Analysis Plan

The co-primary outcome variables will be peak VO₂ and work performed during a symptom-limited maximal effort exercise test. All secondary outcome measures are continuous variables. The predictor of interest for all aims will be intervention (KNO₃ therapy vs. placebo), with analyses based upon the total number of subjects randomized. Initial descriptive estimates of all measures will be generated for study participants at each time point by treatment group. Statistics will include estimates of central tendency, measures of variability, and derived moments of skewness and kurtosis. Analyses of distributional properties will be performed to determine if variance stabilizing or normalizing transformations should be applied. Outliers will be assessed via visual inspection of distributions and checked for accuracy. Aim 1 will assess the effects of potassium nitrate therapy on peak O_2 / work performed (co-primary outcomes) and quality of life score (secondary outcome). An initial assessment of the treatment effect will be performed using the paired t-test and the non-parametric Wilcoxon sign-rank test on the difference between the paired within subject outcome measures. This will be followed by a more comprehensive linear mixed-effects model analysis¹⁵⁸ allowing for assessments of the treatment effect on each continuous outcome of interest while controlling for effects of other covariates such as period, sequence, and a random subject effect nested within sequence. For non-normal distributed outcomes, we will utilize nonparametric methods or consider distribution-stabilizing transformations. The intervention groups will initially be compared within each period (time invariant covariates will only be compared for period 1) according to continuous covariates described above using parametric or non-parametric one-way ANOVA models, depending upon whether or not normality appears to be in question. Levine's tests will be used to assess homogeneity of variance. Additionally, the intervention groups will be compared within period according to categorical covariates using Fisher's Exact tests. Significant differences between groups on these variables will result in their use as control variables in the modeling of outcome. Separate models will be generated for each of the two outcome measures, with each outcome measure regressed on intervention group assignment, along with baseline outcome and any other covariates deemed prognostic in preliminary analyses. The linear mixed-effects models will incorporate adjustments for any period effect and include data from dropouts.¹⁵⁹⁻¹⁶¹ The model will include subject-specific intercepts as random effects, and assumes independent and identically distributed random errors within subject. Restricted maximum likelihood estimation will be used, and an appropriate covariance matrix will be specified. Model assumptions will be examined (eg,QQ plots to assess normally distributed residuals for valid Wald tests). All mixed-effects models will be analyzed using the SAS PROC MIXED procedure¹⁶² in SAS version 9.3 (SAS Institute, Inc., Cary, NC). We will make every possible effort to minimize missing data and ensure final assessments for participants opting to discontinue study participation. Missing data, however, is an inevitable problem in a longitudinal study. The mechanism for missingness-missing completely at random (MCAR), missing at random (MAR), nonignorable or not missing at random (NMAR)-will be evaluated prior to implementing methodology intended to minimize bias from missing data.¹⁶³ We anticipate that ~10% of randomized subjects will not complete the study.

The intent-to-treat principle of including all randomized participants in the outcome models will be followed. SAS software procedures will be used for creating and analyzing multiple imputed data sets for incomplete multivariate data. Instead of filling in a single value for each missing value, Rubin's¹⁶⁴ multiple imputation procedure replaces each missing value with a set of plausible values that represent the uncertainty about the correct value to impute. These multiple imputed data sets are then analyzed using standard procedures for complete data and combining the results from this analysis. Assuming monotone missing data patterns emerge, either a parametric regression method that assumes multivariate normality or a nonparametric method that uses propensity scores will be implemented, depending upon distributional patterns.

Analytic methods described above will take advantage of all available data. The possibility of systematic bias in the outcomes for those who withdraw exists. Baseline characteristics will be compared among subjects with and without complete follow-up, recognizing that statistical power associated with finding true statistical differences may be limited. To assess potential biases, a comparison of withdrawal rates and or/time to withdrawal will be included. If the number of subjects lost to follow-up is small and the missing observations can be documented as being MAR or MCAR, then the primary hypotheses will be tested using the complete observed data. If missing observations cannot be assumed to be MAR or MCAR, more complex approaches will be considered. Sensitivity analyses for these models will be performed should they be implemented.¹⁶⁵

Our secondary aims involve exploratory analyses investigating mechanisms of action. In addition to assessing the effect of our randomized intervention on each mechanistic endpoint, exploratory structural equation modeling will be used to evaluate associations between outcomes and biologic mechanistic pathways. The modeling will be carried out in three sequential steps: (1) exploratory factor analysis, (2) confirmatory factor analysis, and (3) structural equation modeling. The exploratory factor analysis will be based on principal axis factoring to decrease the number of variables. For both theoretical and empirical reasons, it will be assumed that retained factors are correlated and thus an obligue rotation method will be used. Measured and latent variables will be examined for co-linearity, and related variables will be combined into single factors with individual factor loadings. To determine the number of factors, the model will be evaluated against the following four rules: (1) eigenvalues greater than 1.0¹⁶⁶; (2) Glorfeld's¹⁶⁷ extension of parallel analysis, where a large number of random correlation matrices are generated to compare the number of eigenvalues that are significant by chance¹⁶⁸; (3) high internal consistency (an alpha coefficient of \geq .70) for unit-weighted factors,¹⁶⁹ and (4) interpretability.¹⁷⁰ The heaviest weight will be placed on the Minimum Average Partial and parallel analysis methods, with the scree test as a visual adjunct.¹⁷¹ The next step involves incorporating the factors into a model using confirmatory factor analysis. The model will be tested using goodness of fit tests to assess the overall fit of the model to the data. Various models will be tested and compared prior to arriving at the best fitting model. And finally, the best fitting model obtained from confirmatory factor analysis will incorporate a structural equation model designed to examine the links between the randomized intervention, the mechanistic variables and the clinical variables assessed in the trial.

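### The mixed model for the co-primary endpoints takes covariates by significance testing between treatments, with nothing keeping out variables the drug has changed, and it calls for a baseline value that is never measured

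*Combined protocol and SAP*

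**What the plan says.** Section 10.2 starts with simple tests: "An initial assessment of the treatment effect will be performed using the paired t-test", together with a Wilcoxon test on the within-subject differences. It continues: "This will be followed by a more comprehensive linear mixed-effects model analysis". That model has terms for period and sequence and a random subject effect within sequence. It is to "incorporate adjustments for any period effect and include data from dropouts", and the section adds: "The intent-to-treat principle of including all randomized participants in the outcome models will be followed".

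Covariates reach the model by two data-driven routes.

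- **Significance screen.** The intervention groups are to be "compared within each period (time invariant covariates will only be compared for period 1", and this is done "according to continuous covariates described above". Categorical covariates are compared within period by Fisher's exact test. The consequence is mandatory: "Significant differences between groups on these variables will result in their use as control variables in the modeling of outcome".
- **Prognostic screen.** Each outcome is regressed on treatment "along with baseline outcome and any other covariates deemed prognostic in preliminary analyses".

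The only covariates named before the phrase pointing back to them are period, sequence and subject. No significance level is given for the screen, and no rule restricts candidates to values taken before randomization.

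On timing, Section 5.4 describes a one-week washout without a routine assessment. Section 4.3.3 adds an ad hoc visit before phase 2, but only for subjects with flagged findings.

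**The concern.** Sequence is randomized (Section 5.2), so treatment groups can differ within a period for only two reasons: chance, or the drug. A chance difference needs little attention here, because a subject-level covariate such as age or sex cancels within each complete pair. The screen therefore has little to offer where it is harmless. Where it picks up a real difference, it is likely to have found something the drug changed.

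Only time-invariant covariates are confined to period 1, so time-varying ones are screened in both periods. Without a post-washout baseline, their values normally come from the 6-week visits, on treatment. If such a variable is admitted, the treatment coefficient no longer estimates the total effect of KNO₃ unless the variable is unrelated to the outcome within subject. At stake is the estimate for peak VO2 and total work from the model that the text favours.

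A smaller defect sits in the same sentence. The baseline outcome term cannot be fitted for either co-primary endpoint.

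**Working it through.** **1. The plan's own power figure.** Section 10.1 gives a target of 0.6 ml/kg/min, an SD of change of 1.23, 84 enrolled, 90% retention, two-sided alpha 0.05, and 80% power. Completers: 84 × 0.9 = 75.6, so 75 or 76. The standard error is 1.23/√76 = 0.141 and the noncentrality is 0.6/0.141 = 4.25. Noncentral-t power is 98.7% (98.6% with 75). The stated 80% does not reproduce; reading 1.23 as a within-subject SD gives 84%. That discrepancy is a separate matter. Here, 98.7% is the reference for a fixed model.

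**2. Are drug-responsive variables measured?** The pilot results in Sections 3.5.1 to 3.5.4 give shifts relative to the average of the two SDs:

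- fall in vascular resistance: (42 − 32)/18.5 = 0.54
- augmentation index: (141.4 − 132.2)/19.3 = 0.48
- exercise heart-rate rise: (78.0 − 65.6)/22.55 = 0.55

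Section 10.2 names none of these as covariates. They show only that a 0.5 SD shift is not far-fetched in this setting.

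**3. Illustration of the rule.** All of the following is assumed: one covariate with SD 1, shifted 0.5 SD by the drug; correlation r between its two period values of 0.5 or 0.8; 38 completers per sequence. The covariate is t-tested in each period at 0.05. If either test is significant, the within-subject outcome difference is adjusted for the covariate difference as well as sequence. It is selected in 89-95% of runs.

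*Precision.* Adjustment multiplies the variance by 1 + shift²/(2(1 − r)):

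- r = 0.5: 1 + 0.25/1 = 1.25, standard error × 1.12
- r = 0.8: 1 + 0.25/0.4 = 1.625, standard error × 1.27

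*Bias, 25% mediated.* The adjusted model removes 0.25 × 0.6 = 0.15, leaving 0.45 whenever the covariate is selected.

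*Bias, no mediation, within-subject covariate-outcome correlation 0.3.* The SD of the covariate difference is √(2(1 − r)), which is 1.00 or 0.632. The slope is 0.3 × 1.23/SD, which is 0.369 or 0.583. The bias is 0.5 × slope, which is 0.18 or 0.29. The adjusted estimate is 0.42 or 0.31 when selected.

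Under the null, that bias becomes false positives. If the covariate were always adjusted for, the standard errors would be 0.141 × √(1 − 0.09) × 1.12 = 0.151 and 0.141 × √(1 − 0.09) × 1.27 = 0.171. Bias over standard error is then about 1.2 and 1.7. Selection in fewer than all runs lowers the resulting rejection rates slightly.

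Simulated results, averaged over whether the covariate was selected:

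| Assumption | Estimate (true 0.60) | Power | False positives under the null |
|---|---|---|---|
| Fixed model | 0.60 | 98.7% | 5% |
| No shift (selected 8-9%) | 0.60 | 98.7% | about 5% |
| 0.5 SD shift, no path, no correlation | 0.60 | 90-96% | about 5% |
| 0.5 SD shift, 25% mediated | 0.46 | 71-83% | not applicable |
| 0.5 SD shift, correlation 0.3, no mediation | 0.32-0.43 | not tabulated | about 20-37% |

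The signs here pull the estimate down. Opposite signs would push it up: a −25% path gives 0.74-0.75.

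**4. Baseline outcome.** Section 5.1 and Appendix 1 give a 6-minute walk at the initial visit and no maximal exercise test. Sections 5.3 and 5.5 place that test at the two 6-week visits only. Peak VO2 and total work therefore have no baseline. KCCQ does, being given before randomization (Section 8.2).

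**The case against.** The strongest reply is that Section 10.2 never proposes an on-treatment measurement as a covariate. The physiological variables with pilot shifts near 0.5 SD include listed secondary endpoints, and the same section sends mechanistic variables to exploratory structural equation modeling. For ordinary candidates such as age, sex or comorbidity, the rule does almost nothing with complete pairs. The unadjusted paired tests are also specified and would reveal a divergent adjusted result. All of this stands, and it makes the harm conditional. It does not rescue the rule, which is mandatory, has no candidate list, and screens time-varying covariates in both periods.

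Three stronger readings are tempting, and the documents do not support them.

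- A reader might infer that the plan will adjust for mediators. It does not say so; it only fails to exclude them.
- A reader might take the Section 10.2 sentence on testing the primary hypotheses in the complete observed data as setting up a rival primary analysis. It names a data set for the case of limited, ignorable missingness, and a mixed model fits it equally well.
- A reader might treat the missing primary label as an error in itself. The text plainly leans toward the mixed model, so the absent label is missing detail.

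In the other direction, a reader might suppose that bias needs mediation, or that false positives need a mediated effect exactly cancelled by a direct one. Neither is required, as the 0.3-correlation case shows.

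**Conclusion.** The concern holds as a defect in the stated covariate rules. The model favoured for the co-primary endpoints has a covariate set decided by the data, and the selection rule can admit variables because the drug moved them. Precision then falls. The estimate is biased if the variable lies on the causal path or shares a within-subject cause with the outcome.

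The size cannot be established, because the documents give no covariate, correlation or mediated share. Under the assumptions above, the consequence ranges from none (no shift), through a power loss to 90-96% without bias, to an estimate of 0.32-0.46 in place of 0.60. These figures do not show that this trial's result would be biased.

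The baseline outcome point needs no assumption: as written, the term cannot be fitted for peak VO2 or total work.

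**What to change.** For each co-primary endpoint, name one primary analysis: a mixed model with treatment, period and sequence as fixed effects and subject within sequence as random. Then:

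- Delete both data-driven selection rules from that model. If covariates are wanted, list them by name and allow only values taken before randomization.
- Delete the baseline outcome term for peak VO2 and total work. It may stay for KCCQ.
- Label the paired t-test and the Wilcoxon test supportive.
- Keep any model that adjusts for on-treatment variables exploratory, alongside the structural equation modeling.

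The cost is a wording change to Section 10.2. It needs no new data or visits, and on the plan's own inputs the fixed model has about 98.7% power for peak VO2.

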Based on preliminary data demonstrating the effects of a single oral dose of inorganic nitrate in HFpEF, the current trial was designed to assess the efficacy of sustained oral administration of inorganic nitrate in a more diverse and representative sample of HFpEF patients and to further assess the mechanisms by which inorganic nitrate enhances oxygen uptake and exercise capacity. This is a randomized double-blind crossover clinical trial, in which 84 subjects with HFpEF will receive the following 2 interventions, in randomized order: (1) Potassium nitrate (KNO₃), at a dose of 12-18 mmol/d by mouth for approximately 6 weeks, or; (2) Potassium chloride (KCI), at a dose of 12-18 mmol/d by mouth for approximately 6 weeks. A 1-week washout period will be introduced between the 2 interventions. The purpose of the trial is to test the efficacy of KNO₃ on a number of clinical and physiologic endpoints in subjects with HFpEF.

Our specific aims are:

Specific Aim 1: To assess whether KNO₃ therapy improves endpoints with direct clinical relevance: aerobic capacity and quality of life (QOL).

Hypothesis 1a: KNO_3 will improve exercise capacity, quantified as: (1) Total work performed during a maximal-effort exercise test; (2) Peak oxygen consumption (VO₂) during a symptom-limited maximal effort exercise test. These will be the co-primary endpoints of the trial.

Hypothesis 1b: KNO_3 will improve QOL, assessed using the Kansas City Cardiomyopathy Questionnaire.

Specific Aim 2: To dissect the effects of KNO₃ on specific physiologic adaptations to exercise

Hypothesis 2a: KNO₃ improves the systemic vasodilator response to exercise, measured as the change in systemic vascular resistance during a symptom-limited maximal effort exercise test.

Hypothesis 2b: KNO₃ improves muscle blood flow during exercise, measured with flowsensitive PC-MRI during a standardized plantar flexion exercise test.

Hypothesis 2c: KNO₃ improves muscle Cr recovery kinetics (a marker of oxidative capacity), measured with MRI. We will also assess the exercise-induced spatial matching (i.e., within muscle) of blood flow and oxidative capacity using a highly novel method (chemical exchange saturation transfer) that allows, for the first time, for highresolution spatial mapping of Cr in muscle.

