 To assess whether KNO₃ improves quality of life To assess whether KNO₃ improves the systemic vasodilator response to exercise To assess whether KNO₃ improves muscle blood flow during exercise. To assess whether KNO₃ improves muscle PCr recovery kinetics (a marker of oxidative capacity) To assess whether KNO₃ improves LV diastolic function and myocardial systolic strain To assess whether KNO₃ reduces late systolic LV load from wave reflections
 To assess whether KNO₃ improves the exercise-induced spatial matching (i.e., within muscle) of blood flow and oxidative capacity (assessed by chemical exchange saturation transfer). To assess whether KNO₃ has different effects in men vs. women and in African-American vs. non-African American subjects To assess whether KNO₃ improves: Ventilatory threshold, VO₂ kinetics

• Natriuretic peptide levels

	 Physical activity (measured via accelerometry) 24-hour late systolic pressure augmentation, measured with the Aurora device
	4. To assess the relationship between nitrate and nitrite levels achieved and the therapeutic response achieved in each subject (improvement in endpoints in response to KNO ₃ vs. placebo)
Primary Endpoint	Total work performed and peak oxygen uptake (VO₂) during a symptom-limited maximal effort exercise test after approximately 6 weeks of KNO ₃ vs. KCI.
Secondary Endpoints	 Quality of life score, assessed using the Kansas City Cardiomyopathy Questionnaire.
	 The change in systemic vascular resistance reserve during exercise during a symptom-limited maximal effort exercise test.
	 Muscle blood flow during exercise, measured with flow sensitive PC- MRI during a standardized plantar flexion exercise test.
	4. The time constant of Cr recovery after a plantar flexor exercise protocol.
	 Measures of LV diastolic function (E/e', left atrial volume index) and peak global systolic myocardial longitudinal and circumferential strain.
	6. Augmentation index, late systolic wall stress and aortic input impedance.

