10. STATISTICAL CONSIDERATIONS

10.1. Power calculations

We will randomize 84 subjects to one of 2 sequences (i), each of which consists of 2 periods (AB/BA design). We now have pilot data regarding the distribution of the changes in peak VO_2 (the primary endpoint of the study) as well as various secondary endpoints, among patients with HFpEF. We considered an increase in peak VO₂ of \sim 0.6 ml/kg/min to be the minimum clinically significant change. This was based on the fact that even "modest" changes of comparable magnitude in peak VO₂ have been associated with improved outcomes.¹⁵⁶ The standard deviation of the change in peak VO₂ in our pilot trial was 1.23 ml/kg/min. Therefore, the standardized effect size is 0.49 or greater. Assuming a 90% retention rate, enrolling 84 subjects in this cross-over trial will have 80% power to detect such an effect size in the intervention induced change of our study endpoints, with a two-sided α =0.05. Based on the distribution of the changes in study endpoints in our pilot trial or from repeated measurements of the Kansas City Cardiomyopathy Questionnaire in HFpEF patients, we estimated that this trial study is powered (80%) to detect the following changes in other endpoints: 4.6 points for the Kansas City Cardiomyopathy Questionnaire, 8.2% for exercise vasodilatory reserve, 19% for cardiac output reserve, 5 seconds for PCr/Cr recovery kinetics, and 4.2% change in reflection magnitude. We note that these differences are well below what is considered a clinically significant change in KCCQ (10 points or more, http://cvoutcomes.org/pages/3217) or the effect size that has been observed for these endpoints in our pilot trial.¹¹¹ Therefore, we are confident that we will achieve adequate power not only for our clinical endpoints, but also for our physiologic measures. PASS11157 was used to perform power analyses.

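### Peak VO2 and total work are co-primary, but the plan states no success rule or alpha allocation, and it adjusts both for a baseline value that is not collected

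*Combined protocol and SAP*

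**What the plan says.** Section 1 (Hypothesis 1a) lists total work and peak VO2 as two measures of exercise capacity and adds: "These will be the co-primary endpoints of the trial". The synopsis row for the primary endpoint joins them: "Total work performed and peak oxygen uptake". Section 10.2 also calls them co-primary.

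Section 10.1 differs. It describes peak VO2 alone, in a parenthesis, as "the primary endpoint of the study) as well as various secondary endpoints". It then claims 80% power, at two-sided 0.05, "to detect such an effect size in the intervention induced change of our study endpoints". That is the only alpha given for the main trial; the 0.05 threshold in Section 10.4 belongs to the cardiac MRI sub-study.

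Section 10.2 starts with a paired t-test and a signed-rank test, both called initial. Then: "This will be followed by a more comprehensive linear mixed-effects model analysis", with period, sequence and a random subject effect, fitted by REML. On the co-primary endpoints: "Separate models will be generated for each of the two outcome measures, with each outcome measure regressed on intervention group assignment". The plan wants these models to carry further adjustment terms as well, which it gives as follows: "along with baseline outcome and any other covariates deemed prognostic in preliminary analyses". On covariates found to differ between the intervention groups within a period: "Significant differences between groups on these variables will result in their use as control variables in the modeling of outcome".

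**The concern.** With two co-primary endpoints, the trial-level error rate depends on the rule that turns two results into one conclusion. Requiring both and accepting either are different trials in this respect. The plan does not choose, and the single-primary wording in Section 10.1 opens a third reading. If the rule is settled after the results are known, a trial positive on one endpoint only can be reported as a success with no agreed error rate.

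The second issue is the content of the model. The baseline-outcome term needs a pre-randomisation maximal exercise test. The covariate rule lets the data choose what is adjusted for, and it may admit variables measured on treatment. Both leave decisions to the time of analysis.

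**Working it through.** **1. The plan's own power figure.** Inputs from Section 10.1: difference 0.6 ml/kg/min, SD 1.23, 84 randomised, 90% retention. Completers: 84 × 0.9 = 75.6, taken as 76. Standardised effect: 0.6/1.23 = 0.488, matching the stated 0.49. Power of a paired comparison uses the noncentral t with 75 df and noncentrality d√n.

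- If 1.23 is the SD of paired differences: 0.488 × √76 = 4.25, power 98.7%.
- If 1.23 is the within-subject SD, the SD of differences is 1.23 × √2 = 1.74 and d = 0.345: 0.345 × √76 = 3.01, power 84%.

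Neither gives the stated 80%, but both exceed it. That is a separate matter; the two values are used below only to price the fix.

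**2. Error if either endpoint suffices.** Two test statistics, each at two-sided 0.05 (critical value 1.96), no true effect on either endpoint, bivariate normal with correlation ρ. The documents give no ρ, so it is varied.

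- Any false positive: 1 − P(|Z1| < 1.96 and |Z2| < 1.96). At ρ = 0 this is 1 − 0.95² = 0.0975.
- False claim of benefit: 1 − P(Z1 < 1.96 and Z2 < 1.96). At ρ = 0 this is 1 − 0.975² = 0.0494.

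| ρ | either, two-sided | either, benefit | both, two-sided |
|---|---|---|---|
| 0 | 9.75% | 4.94% | 0.25% |
| 0.5 | 9.07% | 4.54% | 0.93% |
| 0.7 | 8.35% | 4.17% | 1.65% |
| 0.9 | 7.04% | 3.52% | 2.96% |

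As ρ approaches 1, the either-suffices rates fall to 5% and 2.5%.

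**3. Error if both are required.** The last column is 5% + 5% minus the either-suffices rate, for example 10% − 9.75% = 0.25%. If one endpoint truly responds and the other does not, the error rises to at most 5% (2.5% for benefit). There is no inflation.

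**4. Is there a baseline value?** Section 5.1 lists a 6-minute walk test at the initial visit but no maximal exercise test. Section 5.3 places the first maximal test at the six-week visit of Phase 1, on treatment. Section 5.4 describes no testing in the washout. By contrast, Section 8.2 collects the KCCQ before randomisation. So the term is unavailable for both co-primary endpoints and available for KCCQ.

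**5. Does covariate selection matter?** Write subject i's outcome in period j as treatment + period + βx + subject effect + error. If x is constant within a subject, the difference between that subject's two periods removes βx. With complete pairs, adding x therefore leaves the treatment contrast essentially unchanged. If x varies by period, β(x1 − x2) stays in the difference. If x was measured on treatment, it may itself be affected by treatment. With incomplete pairs, between-subject information enters and even a constant x can matter. Section 10.2 limits time-invariant covariates to the period 1 comparison, which implies that time-varying ones are compared in each period; it does not list them.

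**The case against.** The strongest reply is that the text leans towards a joint reading. There is one hypothesis about exercise capacity with two measures, and the synopsis joins them with a conjunction; co-primary is often taken to mean that both must succeed. On that reading no error is inflated. This is fair, and it is why the error figures are conditional. It does not settle the matter: naming two endpoints is not a decision rule, and Section 10.1 names only one.

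The range also rests on an assumed correlation. Both measures come from the same exercise test, so values near 0 are unlikely. Section 3.5.1 reports that work and oxygen consumption rose together in the pilot, but that describes mean effects and is not a within-subject correlation.

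A reader might infer that the primary model cannot be fitted. The documents do not support that: Section 10.2 also gives treatment, period, sequence and random subject, which can be fitted; one term is missing. A reader might also infer a free choice among t-test, signed-rank test and mixed model. The first two are called initial and the mixed model is evidently the main analysis, so what is missing is the label. Nor does significance-driven selection disturb the result through every covariate; step 5 limits where it can.

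**Conclusion.** The point holds in conditional form. The absence of a success rule and alpha allocation, and the conflict with Section 10.1, are plain from the text. If either endpoint suffices at two-sided 0.05, false claims of benefit run at 3.5% to 4.9% against 2.5%, or 7.0% to 9.8% two-sided against 5%. This assumes one fixed test per endpoint and a correlation from 0.9 down to 0, with the lower error figures more plausible. If both are required there is nothing to correct beyond saying so. It would be wrong to report 9.8% as the trial's error rate.

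The missing baseline value is certain from the visit descriptions but affects one term. The covariate rule is a real weakness for on-treatment covariates and incomplete pairs; its effect is not quantified here.

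A reader might also infer that total work is underpowered. Section 10.1 gives no SD or target difference for it, so the documents neither show nor exclude this.

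**What to change.** Before unblinding:

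1. Name the Section 10.2 mixed-model treatment contrast (treatment, period, sequence, random subject, REML) as the confirmatory test for each co-primary endpoint. Drop the baseline-outcome term for these two; KCCQ can keep it. Replace significance-driven covariate selection with a pre-specified list that excludes on-treatment covariates.
2. State the success rule. If either endpoint suffices, use Hochberg at two-sided 0.05: claim both if the larger p-value is at most 0.05, otherwise claim the smaller if it is at most 0.025. Simulated under no effect on either endpoint, this gives about 5.0%, 4.8%, 4.6% and 4.2% at correlations 0, 0.5, 0.7 and 0.9. If both are required, test each at two-sided 0.05.
3. Make Section 10.1 agree with the co-primary status.

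This needs wording only, with no added visits, but it affects power. In Hochberg's worst case (alpha 0.025, 76 completers) peak VO2 power goes from 98.7% to 97.4% if 1.23 is the SD of paired differences. If 1.23 is the within-subject SD, it goes from 84% to 76%, below the planned 80%. If both are required and each test had 84% power (illustrative, since none is documented for total work), joint power is about 71%, 75%, 77% and 80% at correlations 0, 0.5, 0.7 and 0.9. The sponsor should choose the rule with those figures in view.
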